#### **6.1.4. Multiplicity**

The study has one primary efficacy endpoint. The secondary efficacy endpoints will be tested sequentially at the 0.05 level to control the overall Type I error rate. Each key secondary endpoint will be tested in pre-specified order.

#### **6.1.5. Handling of Dropouts and Missing Data**

Missing data will be handled as follows:

- For clinical outcome at Day 7, 14, 21, and 28, missing data will be handled using the nearest clinical data available prior to that day, i.e. last observation carried forward (LOCF) approach.
- For microbiological outcome at Day 7, 14, 21, and 28, missing data will be handled using the nearest microbiological data available prior to that day, i.e. **LOCF approach**.
- In cases of missing or incomplete dates [e.g. adverse event (AE) and concomitant medications], the missing component(s) will be assumed as the most conservative value possible. For example, AEs with missing start dates, but with stop dates either overlapping into the treatment period or missing, will be counted as treatment-emergent, taking the **worst-case approach**. When partial dates are present in the data, both a partial start date and/or a partial stop date will be evaluated to determine whether it can be conclusively established that the AE started prior to the start of study drug or ended prior to the start of study drug. If the above cannot be conclusively established based on the partial and/or present dates, then the AE will be considered as treatment-emergent. Actual data values will be presented in the data listings.
- A conservative approach will be taken to assess the relationship of an AE to study drug: if the relationship of an event is missing, it will be considered treatment-related. Missing severity for an AE will not be imputed.
- **Missing values for other variables will not be imputed** and only observed values will be used in data analyses and summaries.

### **6.2. Analysis Populations**

#### **6.2.1. Safety Population**

The Safety Population is defined as all subjects who have received the study drug. All safety data will be analyzed using the Safety Population. In the event that a subject took the wrong study drug (i.e., did not take the randomized study drug), the actual treatment received will be used for analysis.

#### **6.2.2. Intent-to Treat Population (ITT)**

The ITT Population is defined as all subjects who have been randomized and treated with any amount of study drug, regardless of microbiological documentation. Subjects will be analyzed by randomized treatment group.

#### **6.2.3. Microbiological Intent-to-Treat Population (micro-ITT)**

The micro-ITT Population is defined as all ITT subjects for whom microbiological documentation of pneumonia due to *P. aeruginosa* at screening/baseline has been obtained.

The micro-ITT population will be used for efficacy analyses. Subjects will be analyzed by randomized treatment group.

#### **6.2.4. Per-protocol Population (PP)**

The PP Population is defined as all micro-ITT subjects who completed the study without any major protocol deviation. Major protocol deviations may include but are not limited to:

- Have major inclusion or exclusion violations
- Take the wrong study drug (i.e., did not take the randomized study drug)
- Do not have Day 21 assessment unless deemed a treatment failure at an earlier time point
- Receive non-study potentially-effective concomitant antibiotic therapy against *P. aeruginosa* except in case of treatment failure

Based on the above criteria, the validity listings will be provided to identify which subjects to be excluded from the Per-protocol Population (PP). After the study team's review in a blinded manner, the decision to exclude a subject from the PP Population will be finalized and a list of subjects with major protocol deviations leading to exclusion from the PP Population will be finalized and documented prior to unblinding the randomized treatment assignments..

### **6.3. Subject Data and Study Conduct**

#### **6.3.1. Subject Disposition**

Subject disposition will be summarized by treatment group and in total for all randomized subjects. The following subject disposition categories will be included in the summary:

- Subjects who were randomized,
- Subjects who received study drug,
- Subjects who did not receive study drug,
- Subjects who completed the study, and
- Subjects who did not complete the study.

For subjects who did not complete the study, a summary will be provided by reason for discontinuation. Counts and percentages of subjects in each defined analysis population will be tabulated by treatment group and in total based on all randomized subjects.

#### **6.3.2. Protocol Deviations**

The number of subjects with reportable protocol deviations in each category will be summarized by treatment group and in total for the ITT Population. All protocol deviations will be listed by subject.

#### **6.3.3. Demographic and Baseline Characteristics**

The following demographic and baseline characteristics will be summarized:

- Age (years) and age categories (<65 years or ≥65 years);
- Sex;
- Race;
- Ethnicity;
- Height (cm);
- Weight (kg);
- Body mass index (BMI) (kg/m^2) ;
- Randomization stratum 1: VABP or non-VABP;
- Randomization stratum 2: PaO2/FiO2 ≤200 or >200;
- Randomization stratum 3: Americas, Eastern EU, Western EU or Asia;
- Baseline APACHE score: ≥20 and <20;
- Baseline pathogen status: Monopathogen (*P. aeruginosa* only) or Multiple pathogens in baseline culture;
- Baseline pathogen susceptibility for *P. aeruginosa*: Multi Drug Resistant (MDR) or Susceptible for *P. aeruginosa*;
- Reason for admission to ICU at baseline (Trauma or Non-trauma);
- Randomization confirmed method: Rapid test only or Culture confirmed randomization; and
- Time from Pneumonia Diagnosis (days).

Demographic and baseline characteristics will be summarized with descriptive statistics or counts and percentages of subjects as appropriate by treatment group and in total for the ITT, micro-ITT, and PP Populations.

#### **6.3.4. Medical History**

Medical history will be coded to system organ class and preferred term using the Medical Dictionary for Regulatory Activities (MedDRA, Version 19.1). Counts and percentages of subjects with medical history by system organ class and preferred term will be summarized by treatment group and in total based on the ITT Population.

#### **6.3.5. Prior and Concomitant Medications**

Prior and concomitant medications will be coded to anatomical therapeutic chemical (ATC) class and preferred term using the World Health Organization Drug Dictionary (WHO DDE B2 September 1, 2016).

Prior medications are medications used before the administration of the study drug. Concomitant medications are medications that were taken on or after the administration of the study drug.

The counts and percentages of subjects taking prior and concomitant medications by ATC class and preferred term will be summarized by treatment group and in total based on the micro-ITT Population. In addition, the number and percentage of subjects taking prior antibiotics within 48 hours of study treatment will be summarized by ATC class and preferred term for each treatment group.

All prior and concomitant medications and procedures will be listed by subject.

### 6.3.6. Compliance to Study Drug

Compliance with study drug will be summarized and will be defined as the actual dose of study drug taken divided by intended dose multiplied by 100. Percent compliance as a continuous variable and the proportion of patients with <90% and ≥90% compliance will be summarized by treatment group for the Safety and micro-ITT Populations.

## 6.4. Efficacy Analyses

### 6.4.1. Primary Clinical Efficacy Endpoint

#### 6.4.1.1. Primary Analysis

The primary efficacy endpoint is the **proportion of patients** with clinical cure at Day 21 in patients treated with Aerucin® versus the placebo group as assessed by the investigator. The investigators' assessment will be the primary analysis of the primary endpoint.

The proportion of patients with clinical cure rate at Day 21 will be summarized by randomized treatment based on the micro-ITT Population and will be analyzed using a **stratified Cochran-Mantel-Haenszel (CMH) test** based on baseline randomization strata (stratum 1: VABP or non-VABP, stratum 2: PaO2/FiO2 ≤200 or >200, and stratum 3: Americas, Eastern EU, Western EU and Asia). The **P-value** from the stratified CMH test will be presented. Prior to the unblinding, the assessment of each strata and strata combinations with respect to the sample size and the corresponding number of endpoints if any or some strata need to be combined to be able to process with the analysis or an **alternative method is called for (e.g. Fisher's Exact test).**

For the primary analysis, subjects who dropped out or had missing outcome data will be included in the denominator. Missing data will be imputed using the nearest clinical data available prior to that day, i.e. LOCF approach.

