9.3 Statistical Methods

Continuous data will be summarized by means, standard deviations, median, min, and max. Categorical data will be summarized by frequency and percentages.

The primary endpoint of Clinical Cure rate at Day 21 will be analyzed using a stratified Cochran-Mantel-Haenszel (CMH) test. The CMH test will be stratified by baseline randomization strata. Time to Clinical Cure will be analyzed using a stratified log rank test. Other continuous endpoints will be analyzed using an Analysis of Covariance (ANCOVA), with treatment as a main effect, site, and baseline strata as covariates. Treatment by site interaction will be evaluated separately. Secondary endpoints will be analyzed using a sequential procedure in predefined order. Categorical variables will be analyzed using a stratified CMH test.

The primary comparisons for all endpoints will be between the 20 mg/kg dose group and placebo and will be done at 0.05 level of significance. The details of the planned analyses will be provided in the Statistical Analysis Plan.

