### **3.2. Randomization and Blinding**

This is a double-blind, placebo-controlled study. Study subjects will be first stratified as follows:

- Stratum 1: ventilator-associated bacterial pneumonia (VABP) or non-VABP
- Stratum 2: PaO2/FiO2 ≤200 or >200
- Stratum 3: Americas, Eastern EU, Western EU and Asia

Randomization will proceed in a 1:1 ratio, in blocks of 4, for the study overall.

A computer-generated randomization schedule will be used to allocate study treatment according to the above randomization scheme. Upon confirmation of eligibility, the study personnel will be prompted to randomize the study subject using the electronic data capture (EDC) / interactive web-based randomization system (IWRS) system.

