
#### 4. SAMPLE SIZE DETERMINATION

The primary efficacy endpoint is the proportion of subjects with Clinical Cure at Day 21.

It is assumed that the proportion of subjects with Clinical Cure will be 65% in the placebo group, and 85% in the 20 mg/kg dose group. With 69 subjects per group, there will be >90% power for a statistically significant difference at a two-sided 0.05 level of significance. Sample size calculation was performed based on Fisher's Exact test using binomial enumerations (PASS version 14). Assuming a 10% drop-out rate, approximately 154 subjects (77 per group) will be randomized.

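### SAP 6.4.1.1 lets the primary stratified CMH test be replaced by an unstratified Fisher's exact test when strata are thin; the switch is not needed for validity and would cost some power

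*SAP*

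**What the plan says.** Protocol 9.3 names a stratified CMH test for clinical cure at Day 21: "The CMH test will be stratified by baseline randomization strata". It gives no fallback and leaves details to the SAP.

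SAP 3.2 lists three stratification factors: VABP or not, PaO2/FiO2 at or below 200 versus above, and four regions ("Stratum 3: Americas, Eastern EU, Western EU and Asia"). Allocation is 1:1 in blocks of 4, described as applying to the study overall.

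SAP 6.4.1.1 repeats the stratified CMH on these factors in the micro-ITT population. It adds that, before unblinding, strata and their combinations will be assessed for sample size and number of endpoints. Two outcomes are possible: some strata are combined, or an "alternative method is called for (e.g. Fisher's Exact test") is adopted. It gives no numeric trigger, no order for combining strata and no closed list of alternatives.

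SAP 4 sizes the trial on Fisher's test: "Sample size calculation was performed based on Fisher's Exact test using binomial enumerations (PASS version 14").

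**The concern.** With 16 cells the review will probably find thin ones, and the SAP names Fisher's exact test as one response. That test ignores the factors used to randomize. It is also conservative in two arms of this size, so its true size is below the nominal 0.05. If thin cells do not damage the CMH test, the replacement buys nothing and gives up power. It also leaves the identity of the primary test to a judgement without a stated rule.

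**Working it through.** **Inputs from the documents.** Cure rates: "the proportion of subjects with Clinical Cure will be 65% in the placebo group, and 85% in the 20 mg/kg dose group". Alpha: two-sided 0.05. Size and stated power: "With 69 subjects per group, there will be >90% power". Randomized: "Assuming a 10% drop-out rate, approximately 154 subjects (77 per group) will be randomized". Cells: 2 × 2 × 4 = 16.

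**Step 1: the plan's own figure.** Exact binomial enumeration of the two-sided Fisher test at 65% versus 85% gives:

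| Per group | Fisher power | Pearson chi-square power | Difference |
|---|---|---|---|
| 69 | 73.3% | 79.0% | 5.7 points |
| 77 | 78.3% | 83.1% | 4.8 points |

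The stated power above 90% does not reproduce; Fisher's test needs about 104 per group (90.0%). The drop-out step does reproduce: 69 / 0.9 = 76.7, rounded up to 77. The power shortfall is a separate matter. The table matters here because neither test uses strata, so the differences are Fisher's conservatism alone.

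**Step 2: how thin the cells are.** If even, 154 / 16 = 9.6 and 138 / 16 = 8.6 subjects per cell. Any unevenness makes some cells much smaller.

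**Step 3: whether thin cells invalidate the CMH test.** In cell h, with n_h subjects, t_h on active drug, c_h = n_h − t_h on placebo, m_h cures and a_h cures on active drug:

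- E_h = t_h m_h / n_h
- V_h = t_h c_h m_h (n_h − m_h) / [n_h² (n_h − 1)]
- CMH = (Σ a_h − Σ E_h)² / Σ V_h, on 1 degree of freedom.

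The approximation depends on the sums. A cell with one arm or one outcome adds zero to the numerator difference and to the variance. The Mantel-Fleiss check asks that Σ E_h lie at least 5 from its smallest and largest attainable values. At N = 138 with 75% overall cure, the simulated margin had a median of about 14–15 and a 1st percentile of about 9.6.

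**Step 4: size and power by simulation (60,000 trials per setting).** The documents do not give stratum shares or effects, so these are assumptions:

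- VABP share 50%, 80% or 95%.
- PaO2/FiO2 split 50%, 60% or 65%.
- Regions equal, or 15/35/40/10%.
- Odds ratios of the factors for cure: none, moderate (1.5–2) or strong (2–3).

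Blocks were run both nested in strata and not nested, because the SAP wording is unclear. CMH was uncorrected.

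| N, blocks | 16-cell CMH power | Fisher power | Fisher's loss vs 16-cell CMH |
|---|---|---|---|
| 138, nested | 77.3–81.7% | 74.9–75.9% | 2.4–5.7 |
| 154, nested | 82.0–85.8% | 80.0–80.9% | 1.9–4.9 |
| 138, not nested | 74.0–78.3% | 73.1–73.5% | 0.5–5.1 |
| 154, not nested | 78.8–82.8% | 78.1–78.5% | 0.4–4.6 |

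Size with no treatment effect was 0.048–0.052 for 16-cell CMH and 0.031–0.039 for Fisher. Against a CMH collapsed to 4 cells, Fisher lost 3.3–5.5 points at N = 138 with nested blocks. With blocks not nested, it lost 3.9–6.9 points against a collapsed CMH (4 or 2 cells), over both sample sizes.

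Nested blocks usually leave slightly unequal arm totals, which makes Fisher's test less conservative. Exact enumeration at 76 versus 78 gives 80.6% power and size 0.040, against 78.3% and 0.033 at 77 versus 77. This is why Fisher does a little better in the nested rows.

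**Step 5: where the loss comes from.** In one nested setting at N = 154 (VABP 80%, PaO2/FiO2 split 60%, unequal regions), the loss was 2.1 points with no stratum effect, 3.1 with moderate effects and 4.2 with strong effects. The first figure is mainly conservatism; the growth is the cost of ignoring the strata.

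**Step 6: a condition.** The advantage belongs to the uncorrected CMH. In the nested, uneven-share settings at N = 154, a continuity-corrected 16-cell CMH had power 76.6–79.5% against Fisher's 80.0–80.4%. The SAP mentions no correction.

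**The case against.** The strongest reply is that this is a blinded contingency that may never be used. Combining strata comes first in the same sentence, and Fisher's test is only an example. Both points stand: the switch is permitted, not planned.

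A reader might infer that choosing the test after seeing pooled outcome counts inflates type I error. The documents do not support that. The review precedes unblinding, pooled counts by stratum do not show the treatment difference, and Fisher's test errs on the conservative side.

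A reader might also infer that the SAP contradicts the protocol. It does not: Protocol 9.3 leaves analysis details to the SAP, and a sparse-data contingency is such a detail.

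The trial was sized on Fisher's test, so using it loses nothing against the plan's own power basis. That is fair, and the failure of the stated power to reproduce should not raise the weight of this point. The comparison here is between the planned primary test and its named replacement.

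Finally, the loss depends on assumed shares and effects, and with blocks not nested it can be as small as 0.4 points. That also stands. The direction did not change in any setting run with the uncorrected CMH.

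**Conclusion.** The point holds in a limited form. The SAP permits an unstratified Fisher's exact test in place of the stratified CMH when strata are thin, and thin cells are likely. Thin cells do not call for it: the uncorrected 16-cell CMH holds its level, while Fisher's runs at about 0.03–0.04.

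The cost, if the switch is made, is about 2–6 points of power with blocks nested in strata and about 0.4–5 points without nesting. These ranges rest on the 65% and 85% cure rates, on stratum shares and effects that the documents do not give, and on a CMH without continuity correction. It would be too much to read the whole loss as the price of discarding the strata, since part is Fisher's own conservatism. This is an avoidable loss of efficiency and an open-ended rule, not a threat to validity.

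**What to change.** In SAP 6.4.1.1, delete the alternative-method clause and state that the stratified CMH test, without continuity correction, is the primary test. If strata may be combined, set a numeric threshold and a collapsing order before unblinding. The documents do not point to one order, so the choice is the sponsor's. If any fallback is kept, name an exact stratified test rather than the unstratified Fisher test. Fisher's test can be reported as a sensitivity analysis.

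The cost is a small edit to one SAP section, with no new data or subjects. There is one small downside: subjects in one-arm or one-outcome cells contribute no information to the CMH unless strata are combined, which is a good reason to fix the collapsing rule at the same time.

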#### Sensitivity Analyses

Sensitivity analyses of the primary efficacy endpoint will be conducted as follows:

- The proportion of patients with clinical cure at Day 21 will be analyzed based on the PP Population.
- The proportion of patients with clinical cure at Day 21 will be analyzed with missing data imputed as the following. If the last observation of clinical outcome assessment prior to Day 21 is a failure, failure will be carried forward to Day 21. Otherwise, missing outcome at Day 21 will be imputed as 'Indeterminate'.
- The proportion of patients with clinical cure at Day 21 will be analyzed based on observed case.

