1 INTRODUCTION AND BACKGROUND INFORMATION

1.1 Rationale

Nosocomial infections such as hospital associated pneumonia (HAP) and particularly ventilator associated pneumonia (VAP) are a major problem for providers and payers [1,2]. Gram-negative bacteria are responsible for approximately 80% of cases of pneumonia in hospitalized patients (this contrasts with bloodstream infections, for example, which are mainly caused by Gram-positive bacteria, of which methicillin-resistant *Staphylococcus aureus* (MRSA) is the most prominent [3]. *Pseudomonas aeruginosa* (*P. aeruginosa*) causes the majority of multi-drug resistant (MDR) nosocomial infections. Pneumonia accounts for approximately 15% of all hospital-associated infections, and also 27% and 24% of all infections acquired in medical intensive-care units (ICU) and coronary care units, respectively, making it the second most common hospital-associated infection after urinary tract infections. Being intubated and attached to a mechanical ventilator are two of the most common risk factors for infection in ICU patients [4].

Mortality for hospital-associated pneumonia and ventilator-associated pneumonia in particular, is high, e.g., for hospital-associated, pneumonia-attributed mortality rates of 20% to 33% have been reported and ventilator-associated pneumonia accounted for 60% of all deaths due to hospital-associated infections [1]. Direct mortality from HAP is ~50% with about 21% of all HAP caused by *P. aeruginosa* infections [2]. The unmet medical need in VAP treatment is even more acute than in cystic fibrosis (CF), as it is increasingly clear that mortality in VAP is high despite aggressive antibiotic therapies (up to 70%) [1], leading to expensive hospitalization costs (~\$150,000 per patient) [4]. VAP patients are also at a high risk of MDR *P. aeruginosa* infection [1,3].

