- If early termination, reason(s) for early study termination and date thereof. Death is a possible reason for early termination.
- Date of discharge from the ICU (when applicable)
- Date of discharge from the hospital (when applicable)

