9.3.5 Missing data

Assessing microbiological outcome at Day 7, 14, 21 (Primary Efficacy endpoint), and 28 will be done using the nearest microbiological data available prior to that day (last observation carried forward, LOCF).

Missing data for secondary efficacy endpoints will be analyzed using the LOCF approach.

For the purpose of sensitivity analysis, missing data will be imputed using baseline observation carried forward (BOCF) and observed case.

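### With no rule for death at Day 21, the observed-case sensitivity analysis (one of three) is likely to drop subjects who died, and the LOCF primary analysis could count a death as a cure

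*SAP*

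**What the plan says.** SAP 6.4.1.1 makes the investigator's assessment of cure at Day 21 in the micro-ITT population the primary analysis. On incomplete follow-up it states: "For the primary analysis, subjects who dropped out or had missing outcome data will be included in the denominator", and then "Missing data will be imputed using the nearest clinical data available prior to that day, i.e. LOCF approach". There is no exception for death, and SAP 6.1.5 adds none.

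Three sensitivity analyses follow:

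- The first repeats the analysis in the per-protocol population.
- The second carries failures forward: "If the last observation of clinical outcome assessment prior to Day 21 is a failure, failure will be carried forward to Day 21". Any other missing Day 21 outcome becomes indeterminate.
- The third is the one at issue: "The proportion of patients with clinical cure at Day 21 will be analyzed based on observed case".

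Protocol 9.3.5 is the source of the third, saying that for sensitivity purposes "missing data will be imputed using baseline observation carried forward (BOCF) and observed case". It also has no rule for deaths.

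Protocol 6.7 treats death as an exit from the study: "Death is a possible reason for early termination". Survival to the index day is an explicit condition of cure only in SAP Table 2 (Protocol Table 7-1). SAP 5.1 has the independent adjudication committee apply those criteria post hoc; it does not state them for the investigator's assessment.

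**The concern.** In ordinary usage, an observed-case analysis keeps subjects who have an assessment at the time point and carries nothing forward. A subject who dies on Day 10 has an early-termination record from Day 10 and, on that reading, no Day 21 value. The subject is then omitted, although not being cured at Day 21 is known and final.

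This conditions the comparison on an event after randomization. SAP 6.1.3 lists better survival as the trial's second hypothesis, and all-cause mortality is a ranked secondary endpoint, so the plan itself expects treatment to affect who remains. A sensitivity analysis meant to test missing-data handling would instead compare survivors. A drug that keeps sicker patients alive but not yet cured would look worse on it, and a drug that raised mortality among uncured patients would look better.

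The gap is wider than this one analysis. Because LOCF has no exception for death, a subject called cured at Day 14 who dies on Day 18 can enter the primary analysis as cured at Day 21.

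**Working it through.** **Inputs from the plan.** SAP section 4 gives cure rates of 65% (placebo) and 85% (active) and 77 randomized per group, which is 69/0.9 = 76.7, rounded up. The stated power plays no part in this point.

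**Assumed inputs.** Death rates by Day 21 are not in the documents. Protocol 1.1 says "pneumonia-attributed mortality rates of 20% to 33% have been reported", but that concerns hospital-associated pneumonia generally and is not a Day 21 rate for this trial. The pairs below are illustrations. If death is a non-cure, 85% cure leaves room for at most 15% deaths on active.

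**Formula.** Let c be the proportion cured among all subjects, with death as a non-cure, and d the proportion dead by Day 21. If no death has a Day 21 assessment and nothing else is missing, the observed-case rate is c/(1 − d).

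| c, placebo / active | d, placebo / active | Observed case, placebo | Observed case, active | Gap, deaths kept | Gap, observed case |
|---|---|---|---|---|---|
| 65% / 85% | 20% / 10% | 0.65/0.80 = 81.25% | 0.85/0.90 = 94.4% | +20 | +13.2 |
| 65% / 85% | 10% / 10% | 0.65/0.90 = 72.2% | 0.85/0.90 = 94.4% | +20 | +22.2 |
| 65% / 85% | 10% / 5% | 0.65/0.90 = 72.2% | 0.85/0.95 = 89.5% | +20 | +17.3 |
| 65% / 65% | 24% / 12% | 0.65/0.76 = 85.5% | 0.65/0.88 = 73.9% | 0 | −11.7 |

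**Subjects lost.** In the first row, 77 × 0.20 = 15.4 placebo and 77 × 0.10 = 7.7 active subjects drop out. In whole subjects, 50/77 against 65/77 (Fisher two-sided p = 0.009) becomes 50/62 against 65/69 (p = 0.030).

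**When the sign reverses.** A true advantage appears as a disadvantage when the ratio of cure rates, active to placebo, is below the ratio of survival rates. With deaths of 24% and 12%, the survival ratio is 0.88/0.76 = 1.158. Against 65% on placebo, any true active rate between 65% and 65% × 1.158 = 75.3% would show as worse than placebo.

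**Masked harm.** Suppose 76.5% of survivors are cured in both arms and deaths are 15% on placebo and 25% on active. Observed case shows no difference. Counting deaths as non-cures gives 0.765 × 0.85 = 65.0% against 0.765 × 0.75 = 57.4%, a deficit of 7.6 points on active.

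**Primary analysis.** The number of subjects called cured who then die before Day 21 cannot be derived from the documents. Each one carried forward as cured raises that arm's rate by 1/77 = 1.3 points.

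**Text comparison.** The per-protocol rule in SAP 6.2.4 counts as a major deviation subjects who "Do not have Day 21 assessment unless deemed a treatment failure at an earlier time point". That clause protects earlier failures from exclusion for an absent Day 21 assessment. The observed-case sentence has no counterpart.

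**The case against.** The strongest reply is that the removal of deaths is inferred. Observed case is undefined, and the schedule of assessments places a cure assessment at the early-termination visit. Protocol 6.7 also requires the final clinical outcome to be documented there. If that record is read as an observed non-cure at Day 21, subjects who died stay in. This stands in part: a reader might infer that everyone who dies before Day 21 necessarily leaves the denominator, and the documents do not settle that. They leave it open, and the usual meaning of the term points to omission.

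A reader might also infer that this analysis is the only check on the primary result. It is one of three, and the second retains subjects who died after a recorded failure. The adjudicated analysis requires survival, and SAP 6.4.2.2 tests mortality by Day 21 directly, so a survival harm would be visible elsewhere. That limits the consequence. It does not make the observed-case result interpretable. Nor are the other two analyses fully protected: per-protocol membership requires completing the study, and the SAP does not say whether indeterminate outcomes stay in the denominator.

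A third tempting inference is that LOCF already classifies deaths correctly, so that only the observed-case analysis needs attention. That holds for deaths after a recorded non-cure. It fails for a cure followed by death, and no document gives the share of each.

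The death rates are chosen for illustration, and the trial excludes moribund patients and caps APACHE II at 35. The scenario with equal cure requires mortality to halve with no gain in cure, which departs from the design assumption. With the planned effect and 20% against 10% deaths, the direction is kept and the result remains below 0.05. These are fair limits on the size. The analysis also carries no alpha.

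**Conclusion.** The point holds in a bounded form. Under the usual meaning of observed case, subjects who die before Day 21 without a Day 21 assessment drop out, and nothing in either document prevents it. At the planned cure rates, the assumed death rates move a 20-point contrast to between about 13 and 22 points. Where the true cure difference is small and deaths are unbalanced, the sign can reverse. These figures assume that no subject who died was cured, that there is no other missing outcome, and that the death rates are as labelled.

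The underlying fault is the missing death rule for the investigator-assessed endpoint, which also leaves the LOCF primary analysis open to counting a later death as a cure. The size of that effect is unknown, at 1.3 points per subject in an arm of 77. The change should be made, but the observed-case analysis alone does not threaten the trial's main conclusion.

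**What to change.** Add one rule to SAP 6.1.5 and refer to it in 6.4.1.1: a subject who dies on or before the index day is an observed non-cure at that day and remains in the denominator, in the primary analysis and in every sensitivity analysis, whatever was recorded earlier. Then define observed case as omitting only subjects who are alive, or whose vital status is unknown, and who have no cure assessment at that day. Apply the same rule to cure at Days 7, 14 and 28, and align Protocol 9.3.5.

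Amending only the observed-case sentence would not be enough. Death would then be a non-cure in a sensitivity analysis and possibly a cure in the primary one, and the two would differ for reasons unrelated to missing data.

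The cost is a few lines in the SAP, to be settled before database lock. Mortality by Days 7, 14, 21 and 28 is already to be tabulated, so no new data are needed. The downside is slightly lower cure rates in both arms.
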